6.3 EXPLORATORY OBJECTIVE

Evaluate the baseline value of hepcidin through ELISA at 12 and 24 weeks, in relation to treatment response.

7 LABORATORIES

Hemoglobin levels will be analyzed at each center's local laboratory.

Anti-erythropoietin antibodies and hepcidin level will be analyzed at BIOSIDUS S.A. located at [name].

8 STUDY DESIGN

This is a multicenter, open - label, randomized and comparative phase IIIB study of two epoetins alfa (HEMAX PFS versus EPREX/ ERYPO®).

Patients older than 18 years with predialysis chronic renal failure (CRF) defined by a glomerular filtration rate through the Modification of Diet in Renal Disease Study formula that is ≥ 15 ml/ min by 1.73 m_2 and < 60 ml/ min by 1.73 m_2 , with an indication of treatment of anemia and levels of hemoglobin < 10.5 g/ dl, which have not received prior treatment with an erythropoiesis stimulating agent in the last 3 months.

The patients that meet all the inclusion criteria and none of the exclusion criteria will be randomized in a 1:1 ratio with stratification by gender to receive HEMAX® PFS or EPREX/ ERYPO® subcutaneously with an initial dose of 29 IU/ kg twice a week (2000 IU twice a week for 70 kg of weight), to be titrated according to the scheme that is summarized in Section 7.

There will be a follow - up of patients with visits to the site every two weeks during the first 12 weeks of dose titration that will be followed by 12 additional weeks of dose maintenance with visits every 4 weeks.

9 STUDY POPULATION

Patients with kidney disease and predialysis chronic renal failure (CRF) with indication of treatment of anemia and levels of hemoglobin < 10.5 g/ dl that have not received previous treatment in the past three months with an erythropoiesis stimulating agent.

9.1 PATIENT NUMBER

There are plans to recruit 120 patients in total that will be randomized in a 1:1 ratio to receive HEMAX PFS (n = 60) or EPREX/ ERYPO® (n = 60).

9.2 INCLUSION CRITERIA

Patients must meet all of the following inclusion criteria to be eligible for the study:

- 1) Patients between 18 and 85 years of age of both sexes.
- 2) IRC defined by the glomerular filtration rate through the Modification of Diet in Renal Disease Study (MDRD) formula that is ≥ 15 ml/ min and < 60 ml/ min by 1.73 m_2 .
- 3) Anemia with indication of treatment and hemoglobin lower than 10.5 g/ dl and greater

than 7.5 g/ dl.

- 4) Patients who have both the will and the capacity to give informed consent in writing.
- 5) Women with at least 2 years of menopause or surgically sterile 6 months ago or of childbearing potential that have a negative pregnancy test during the baseline visit and are willing to receive an effective birth control method (diaphragm or prophylactic associated with a spermicide since at least 21 days before the first treatment; or intrauterine device in place for at least 3 months before the first dose of epoetin alfa: or hormonal birth control method, in pills, patch or implant, initiated at least 3 months before the first treatment).

9.3 EXCLUSION CRITERIA

Any of the following criteria exclude the patient from participating in the study:

- 1) Patient with scheduled entry to dialysis or kidney transplant in the next 6 months.
- 2) Transferrin saturation < 20%.
- 3) Cause of renal failure (as the secondary ones to autoimmune diseases) that in the opinion of the physician may affect the normal development of the Protocol.
- 4) Active bleeding or history of hemorrhage that has caused significant decrease of hematocrits in the last 30 days.
- 5) Uncontrolled hypertension (≥ 160 mm Hg systolic pressure and/ or ≥ 100 mm Hg diastolic pressure with anti - hypertensive treatment).
- 6) Anemia due to another cause other than the kidney disease.
- 7) Transfusion in the last 3 months before the baseline or screening visit.
- 8) Treatment with an erythropoiesis stimulating agent in the 3 months prior to the baseline or screening visit.
- 9) Increased risk of thromboembolic disease: Previous history of arterial thromboembolism (CVA, TIA, Acute Coronary Syndrome or other) in the last 6 months or venous thrombosis in the last twelve months prior to the baseline visit; surgery in the last month prior to the baseline visit; prolonged standstill or orthopedic surgery scheduled in the next

6 months or any other factor which in the opinion of the investigator may increase the risk of thromboembolism in the patient.

- 10) Hematological disease, including myelodysplastic syndrome or a history of hematologic neoplasia or solid tumor in the last 5 years.
- 11) History of congestive heart failure.
- 12) Pregnancy or breast - feeding.
- 13) Refusal of patient to participate in the protocol or patients with a medical condition that the investigator considers significantly relevant to prevent their participation in the study.

9.4 EARLY TREATMENT TERMINATION

The termination visit should be performed in all patients that completed the study prematurely. Patients who decide not to continue with the visits must perform the termination visit before completion. A patient may leave or be excluded from the study due to the following reasons:

- Death.
- Adverse event that in the opinion of the investigator requires early withdrawal (specify principal AE in the AE form).
- Revocation of informed consent.
- At the request of the investigator or physician primarily responsible for the care of the patient.
- Due to major protocol violation that required discontinuation.
- Loss of follow - up, including the fact that patient does not return to the site.
- Positive pregnancy test at any time during the study.
- Patient transfusion or lack of response after 12 weeks of treatment.
- If after twelve weeks the hemoglobin did not increase during the titration phase by at least 1 g/dL from baseline, the patient will be withdrawn from the study.

10 MEDICATIONS/ TREATMENT AND CONCOMITANT MEDICATIONS

10.1 MEDICATION/ TREATMENT

HEMAX PFS or EPREX/ ERYPO® (both epoetin alfa) at an initial dose of 29 IU/ kg twice a week

subcutaneously (2000 IU twice a week for 70 kg of weight) during the 12 weeks of titration, followed by an equivalent weekly dose during the additional 12 weeks of maintenance.

Usual titration scheme and dose management during the titration phase:

- If the hemoglobin in any visit increases >1 g/ dl in any period of 2 weeks prior to the visit, the dose will be reduced by 25%.
- If the hemoglobin, in any visit, increases to values equal to or greater than 11.5 g/ dl the dose will be interrupted and resumed when the hemoglobin drops below 10.5 g/ dl, with a dose decrease by 25%.

Only every four weeks (weeks 4 and 8) from treatment initiation and during the titration period, the dose may be increased according to the following scheme:

- If after four or eight weeks, hemoglobin does not increase by at least 1 g/ dl as compared to the baseline value, the dose will be increased by 25%.
- If after twelve weeks, hemoglobin did not increase during the titration phase at least 1 g/ dl as compared to the baseline value, the patient will be withdrawn from the study.

Maintenance phase:

Patients who have experienced during the titration phase an increase of the Hb of at least 1 g/ dl as compared to the baseline value, will enter the maintenance phase after week 12 until week 24, with visits every 4 weeks. All patients will be switched to a weekly dosing scheme in which they will receive the same total dose of epoetin alfa administered at the end of the titration phase (for example the patients who at the end of the titration phase are with 2000 IU twice a week will receive 4000 IU weekly during the maintenance phase). During the maintenance phase, the following medication adjustments may be performed:

- If despite receiving the indicated dose of epoetin alfa, the Hb drops below 10.5 g/ dl, the dose may be adjusted by 25%.
- If the hemoglobin, in any visit, increases to values equal to or greater than 11.5 g/ dl, the dose will be interrupted and resumed when the hemoglobin has dropped below 10.5 g/ dl, with a dose decrease by 25%.

[figure not shown]
Application of Medication:

According to the above titration scheme the different medication presentations described in section 9.5 will be used to facilitate application and avoid risks related to potential overdosing. During the titration phase, responder patients (hemoglobin increases greater than 1 g/dL) who require a dose reduction may receive the reduced dose in a single weekly application in order to facilitate application and avoid the

potential risks of overdosage. In the (rare) cases in which the patient has sustained hemoglobin increases greater than 1 g/dL and requires doses less than 1000IU/week, the dose will be suspended and restarted at 1000IU/week when the hemoglobin is < 10.5 g/dL to avoid the potential risk of overdosing in responders.

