6 STUDY OBJECTIVES

The study has as a general objective the evaluation of the efficacy and safety of HEMAX PFS compared with EPREX/ ERYPO®, following a dose titration and maintenance scheme similar to that used in the clinical practice in our country, being the specific objectives the following.

6.1 PRIMARY OBJECTIVES:

Evaluate the efficacy of treatment with epoetin alfa through increased levels of hemoglobin from baseline value to the mean value of the 8 to 12 weeks of treatment, comparing patients treated with HEMAX PFS versus those treated with EPREX/ ERYPO®.

Evaluate the safety through the incidence of adverse events and adverse reactions after 12 and 24 weeks of treatment, comparing patients treated with HEMAX PFS versus those treated with EPREX/ ERYPO®.

6.2 SECONDARY OBJECTIVES:

Evaluate the efficacy of treatment with epoetin alfa through the percentage of responder patients (increase of Hb \geq 1g/ dl) after 12 weeks of treatment, comparing patients treated with HEMAX PFS versus those treated with EPREX/ ERYPO®.

Evaluate the percentage of transfusion requirement after 12 weeks of treatment, comparing patients treated with HEMAX® PFS versus those treated with EPREX/ ERYPO®.

Evaluate the intragroup efficacy (HEMAX® PFS and EPREX/ ERYPO®) of treatment with epoetin alfa through increased levels of hemoglobin from baseline in each one of the intermediate visits until the week 12 visit.

Evaluate the intragroup efficacy (HEMAX® PFS and EPREX/ ERYPO®) of the change from the twice - a - week dosing during the titration phase to a weekly dosing during the maintenance phase through the variation of the hemoglobin levels from week 12 to weeks 16, 20 and 24.

In addition, at week 12 and 24 visits, an anti - erythropoietin antibody dosing will be performed to evaluate treatment immunogenicity.

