8.2 Secondary Efficacy Analyses

- Percentage of responder patients (increase of Hb \geq 1g/ dl) after 12 weeks of treatment, comparing patients treated with HEMAX PFS versus those treated with EPREX/ ERYPO®.
- Percentage of transfusion requirement after 12 weeks of treatment, comparing patients treated with HEMAX PFS versus those treated with EPREX/ ERYPO®.
- Intragroup efficacy (HEMAX PFS and EPREX/ ERYPO®) of treatment with Epoetin Alfa through increased levels of hemoglobin from baseline in each one of the intermediate visits until the week 12 visit.
- Evaluate the intragroup efficacy (HEMAX PFS and EPREX/ ERYPO®) of the change from the twice - a - week dosing during the titration phase to a weekly dosing during the maintenance phase through the variation of the hemoglobin levels from week 12 to the weeks 16, 20 and 24.

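### The week 12 schedule-switch analysis may include patients already on weekly injections, and SAP 8.2 does not separate them

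*Protocol*

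**What the plan says.** Protocol 6.2 sets a secondary objective on the within-arm effect of changing schedule, measured "through the variation of the hemoglobin levels from week 12 to weeks 16, 20 and 24". Protocol 16.5 and SAP 3.2.2 and 3.2.3 repeat it. SAP 8.2 carries it into the analysis as an evaluation of "the change from the twice - a - week dosing during the titration phase to a weekly dosing during the maintenance phase".

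Protocol 10.1 admits to maintenance only "Patients who have experienced during the titration phase an increase of the Hb of at least 1 g/ dl as compared to the baseline value". It then says: "All patients will be switched to a weekly dosing scheme in which they will receive the same total dose of epoetin alfa" they had at the end of titration.

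Under Application of Medication, the same section makes an exception before week 12. Under it, certain patients "may receive the reduced dose in a single weekly application". The exception covers responders, meaning a rise above 1 g/dl, whose dose has to come down while they are still in titration. One trigger for a reduction in titration is haemoglobin that "increases >1 g/ dl in any period of 2 weeks prior to the visit, the dose will be reduced by 25" per cent. Another is resumption, at a reduced dose, after an interruption at 11.5 g/dl or above.

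**The concern.** The objective makes sense only for patients who are on two injections per week up to week 12 and on one afterwards. A patient who used the exception and was still on it at week 12 continues on the same schedule. That patient's later haemoglobin says nothing about a change of frequency, yet would be counted as evidence on it.

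Protocol 5 names local evidence on this dosing scheme as a purpose of the study. If the week 12 to 24 course is reported as the result of the switch, part of it may come from patients who did not switch, and the reader would have no means of telling how much.

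**Working it through.** **Is there a figure to reproduce?** No. The sample size in Protocol 16.1 and SAP 5 concerns only the between-arm comparison at weeks 8 to 12. The switch objective has no stated effect size, margin or power, so the check is mainly one of text.

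**Do the two groups overlap?** The exception covers responders with a rise above 1 g/dl who need a reduction. Maintenance takes patients with a rise of at least 1 g/dl from baseline. Patients who used the exception therefore come from essentially the same pool as those analysed after week 12.

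**Does anything in the plan separate them?**
- SAP 8.2 has no restriction, stratification or sensitivity analysis by schedule before week 12.
- The major deviations in SAP 7.2 do not include early weekly dosing. The protocol permits it, so a per-protocol restriction would not remove these patients.
- The dose summaries in SAP 7.6 are weekly and cumulative IU. Injections per week are not listed.
- Patients interrupted at week 12 because haemoglobin reached 11.5 g/dl are a third group. They have no current schedule to switch from, and they are not separated either.

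**How large could the effect be?** Let f be the share of maintenance patients already on weekly dosing at week 12, S the mean change in true switchers, and W the mean change in already-weekly patients. Then

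pooled change = (1 - f) × S + f × W.

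The documents give none of f, S or W, so all values below are assumptions.

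With S = -0.5 g/dl and W = 0:
- f = 0.20: 0.80 × (-0.5) = -0.40
- f = 0.30: 0.70 × (-0.5) = -0.35
- f = 0.50: 0.50 × (-0.5) = -0.25

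With S = -0.5 g/dl and f = 0.30, letting W vary:
- W = +0.5: -0.35 + 0.15 = -0.20
- W = 0: -0.35
- W = -0.5: -0.35 - 0.15 = -0.50
- W = -1.0: -0.35 - 0.30 = -0.65

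The pooled figure can therefore be smaller than, equal to or larger than the effect in true switchers.

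**How many patients does it take?** SAP 5 reports 43 enrolled, 23 and 20 by arm. The maintenance groups can be no larger, so each already-weekly patient is at least 1/23 = 4.3% or 1/20 = 5.0% of an arm.

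**The case against.** **The exception is optional and its use is unknown.** This stands. The documents do not say how many patients used it, and the number may be zero.

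**The direction cannot be claimed.** A reader might infer that the analysis is pulled toward no change, so that a flat course would falsely reassure about weekly dosing. The documents do not support this. It requires already-weekly patients to have zero mean change after week 12, and these are patients with a fast rise or a recent dose reduction. Their haemoglobin may drift for those reasons, up or down.

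**Restricting the set does not isolate the switch.** This also stands. Both arms move to weekly dosing, and no concurrent group stays on two injections. Protocol 10.1 also allows dose adjustments and interruptions in maintenance that steer haemoglobin whatever the schedule. Patients still on two injections at week 12 are selected partly by their response after randomisation.

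**An all-entrants summary is a legitimate description of the regimen as used.** Protocol 5 can be read that way, which is a reason to keep the summary. It does not make that summary an answer to the narrower question, which both documents word as a change of schedule.

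**It is late to redefine a secondary analysis.** SAP 5 describes an interim analysis whose results were already known in this open-label trial. That argues for an added, labelled analysis rather than a replacement. SAP 8.2 also names no population for this analysis, so pooling of prior schedules is what its silence implies, not something it states.

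**Conclusion.** The point holds in a limited form. Protocol 10.1 contradicts itself on whether every maintenance patient changes schedule at week 12, and SAP 8.2 evaluates the change without checking who had one. Neither the deviation list nor the planned dose summaries would reveal it.

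The size is unknown. The -0.40, -0.35 and -0.25 g/dl figures are one scenario, resting on an assumed -0.5 g/dl effect, assumed shares and zero change in already-weekly patients. They are not estimates for this trial.

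The primary comparison at weeks 8 to 12 is not affected. No criterion for maintained haemoglobin is set for this objective, so what is at stake is how a secondary within-arm result is interpreted. It is still worth correcting, because the correction is cheap and lets the analysis address its own stated question.

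**What to change.** In SAP 8.2:
- Derive injections per week at the end of titration from the dose record cards. SAP 7.6 says that these hold date and dose.
- Report by arm how many maintenance patients were on two injections per week, already on one, or interrupted at week 12.
- Keep the all-entrants summary of the change from week 12 to weeks 16, 20 and 24.
- Add the same change in patients whose last titration schedule was twice weekly, labelled as added after the interim analysis. Rest any conclusion about the schedule switch on this group, and show the other two groups descriptively.

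The universal switch and the titration exception in Protocol 10.1 must also be reconciled with the objective. Which dosing rule should apply is for the sponsor to settle.

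The cost is SAP wording and one derived variable, with no new data collection. The downside is a smaller subset in a trial of 43 patients, selected on response after randomisation, in a within-arm comparison that remains uncontrolled. The report should say so.

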5 CURRENT STUDY RATIONALE

In order to obtain more scientific evidence on the use of epoetin alfa in the context of the current treatment of anemia in patients with predialysis CKD, it is of interest to perform a randomized study of HEMAX® controlled with a reference medication such as EPREX/ ERYPO®.

Based on this context and to conform to the current recommendations, we designed a study that will include patients with clinical indication for treatment and levels of hemoglobin <10.5 g/ dl with dose adjustment in aliquots of 25% and interruption of treatment if the Hb reaches values equal to or greater than 11.5 g/ dl so as to maintain the hemoglobin concentration between 10.4 and 11.4g/ dl. Patients with increased thromboembolic risk will be excluded from the study.

The initial dose of epoetin alfa currently recommended for treatment initiation in patients with predialysis CKD are 50 - 100 IU/ kg three times a week subcutaneously. However, these doses are not the ones used in the usual clinical practice in our country, where treatment is initiated with lower doses of 20 to 40 IU/ kg twice a week. This therapeutic approach has the advantage of being more in line with the current recommendations, exposing the patient to lower initial doses, in addition to the convenience to the patient of administering the medication only twice a week instead of three times a week. In addition, it is frequent during the maintenance phase or even from the start to administer epoetin in a single weekly dose. This dosing scheme is founded on that the clinically relevant pharmacodynamic effect of epoetin alfa does not depend on its plasma half - life but on the half - life of the red blood cells. Several clinical studies have demonstrated the equivalence and safety of epoetin administration schemes weekly, every two weeks and every 3 weeks^{17 - 23}.

It is interesting to note that the mean weekly dose of epoetin alfa used in more recent studies has been 5000 ± 2500 IU/ week, a dose that is in the range of our initial dose²⁴.

For these reasons, our study will use a scheme that is frequently used in the practice in our country using lower initial doses administered twice a week subcutaneously in the initial titration phase of 12 weeks, switching then to the same weekly dose but administered once a week during the maintenance phase. Thus, local additional evidence on the efficacy and safety of this dosing scheme will be obtained.

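### Protocol 10.1 permits once-weekly dosing before week 12 for some responders, so the planned twice-weekly-to-weekly switch analysis can include patients who do not switch at week 12

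*Protocol*

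**What the plan says.** Protocol 10.1 gives the titration regimen as "subcutaneously (2000 IU twice a week for 70 kg of weight) during the 12 weeks of titration", followed by an equivalent weekly dose. The synopsis row on route and dosage agrees. The rationale (Protocol section 5) describes "lower initial doses administered twice a week subcutaneously in the initial titration phase of 12 weeks, switching then to the same weekly dose". For maintenance, Protocol 10.1 and the synopsis both state that "All patients will be switched to a weekly dosing scheme in which they will receive the same total dose of epoetin alfa".

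Under the application sub-heading, Protocol 10.1 then adds that, within the titration phase, responders with a rise above 1 g/dl who need a reduction "may receive the reduced dose in a single weekly application in order to facilitate application". The synopsis dosing scheme does not carry this option.

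Protocol 6.2 sets a secondary within-arm objective on "the change from the twice - a - week dosing during the titration phase to a weekly dosing during the maintenance phase". It is measured by how haemoglobin moves after week 12, at weeks 16, 20 and 24. Protocol 16.5 and SAP 8.2 repeat it. None of the three says how to handle a patient already on weekly dosing at week 12. SAP 7.6 summarises epoetin in IU per week and cumulatively, but not by injection frequency.

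**The concern.** The analysis is named for a change of schedule at week 12, but the plan lets some of the analysed patients make that change earlier. The groups overlap by construction. The option is for a rise above 1 g/dl with a dose reduction, and maintenance requires a rise of at least 1 g/dl. A patient who took the option and entered maintenance contributes a change from week 12 with no switch in it.

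Including such patients pulls the estimated switch effect toward no change. They are not a random subset either, because eligibility depends on response and use of the option is a choice made in an open-label trial. Protocol section 5 wants local evidence on this dosing scheme, so it matters whether the analysed patients actually changed schedule when the analysis says they did.

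**Working it through.** The plan gives no figure for this point, so there is none to reproduce. The check has three steps.

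**1. Trace a patient through the text.** The patient starts twice weekly, rises by more than 1 g/dl, has the dose reduced and takes it once weekly (Protocol 10.1, application paragraph). At week 12 the rise is at least 1 g/dl, so the patient enters maintenance (10.1) on weekly dosing. Protocol 16.5 and SAP 8.2 analyse the change from week 12 with no exclusion, subgroup or covariate for earlier frequency. The patient is counted as switched, but the schedule did not change.

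The protocol's own figures make use of the option plausible. A 25% cut from 2000 IU is 2000 × 0.75 = 1500 IU per injection, or 3000 IU per week. Protocol 13.5 lists syringes of 1000, 2000, 3000 and 4000 IU, so the weekly total fits one syringe and the half-dose does not. Uneven twice-weekly injections could also deliver it, so this says nothing about how often the option was used.

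**2. Dilution.** Let p be the share already on weekly dosing, with no switch effect after week 12 in that share. Then:

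- observed switch effect = (1-p) × true effect
- factor on the n needed to detect it = 1/(1-p)²

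| p (assumed) | observed / true | factor on n |
|---|---|---|
| 0 | 1.00 | 1.00 |
| 10% | 0.90 | 1.23 |
| 20% | 0.80 | 1.56 |
| 30% | 0.70 | 2.04 |
| 50% | 0.50 | 4.00 |

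This concerns only the part of the change caused by the switch. Other drift in haemoglobin after week 12 is not covered.

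**3. How large could p be?** The 10.1 rules were simulated with 100,000 patients per scenario. All of these inputs are assumptions, because the documents give none of them: baseline mean 9.0 to 9.8 g/dl (SD 0.7); rise 0.10 to 0.20 g/dl per week (SD 0.15 between patients); fall of 0.15 g/dl per week while dosing is interrupted; haemoglobin error SD 0.15 to 0.4. Eligible means on drug at week 12 after a reduction made while more than 1 g/dl above baseline.

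| Error SD | eligible, of all entrants | eligible, of entrants on drug at week 12 |
|---|---|---|
| 0.15-0.2 | about 1-6% | about 2-16% |
| 0.3-0.4 | about 12-35% | about 30-64% |

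The error SD drives the result. The assumed true two-week rise averages 2 × 0.10 = 0.2 to 2 × 0.20 = 0.4 g/dl, while the reduction trigger is above 1 g/dl in two weeks. The error SD of a difference between two readings is √2 × 0.15 = 0.21 at the low end and √2 × 0.4 = 0.57 at the high end. Much of the simulated eligibility at the high end is therefore measurement noise.

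Eligibility is also not use. p equals eligibility times uptake, and uptake is unknown. At zero uptake p = 0. At full uptake p is about 2% to 64% of on-drug entrants.

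**The case against.** The best answer is that this is a rule with an exception. Protocol 10.1 presents its scheme as the usual one, and the application paragraph builds on it with a permissive provision. Read that way, the dosing text does not contradict itself, and that reading is reasonable. It does not help the analysis, because the sentence switching all patients and the switch objective were not adjusted for the exception.

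The objection on size also stands. With a small error SD few patients are eligible, and nothing shows how many used the option. A reader might take the upper rows at half uptake (0.5 × 30% = 15% to 0.5 × 64% = 32%) as the expected loss. That is only the upper part of an assumed range that starts at zero.

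Three stronger readings are tempting and not supported:

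- **Bias in the primary comparison over weeks 8 to 12.** The option is the same in both arms, both products come in the same syringe strengths (Protocol 13.5), and no mechanism for unequal use is shown beyond the open label.
- **That the affected patients are the fast responders.** In the simulation, eligibility comes largely from assumed measurement error.
- **That SAP 4.1 also contradicts the option.** It gives only an initial twice-weekly dose and no switch. Likewise, the objective in the synopsis states an aim, not a rule that every patient switches.

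Finally, the analysis is secondary and within-arm, with no margin or success rule. Dilution would blur a description; it would not flip a pre-set decision.

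**Conclusion.** The point holds for the secondary switch objective. Followed as written, the plan can include patients with no schedule change at week 12 and report their haemoglobin change as the effect of switching. The shrinkage to (1-p) is arithmetic, given no switch effect after week 12 in the share p. If a move made late in titration still acts after week 12, the dilution is smaller.

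The size cannot be settled from the documents. The eligible share of on-drug entrants runs from about 2% to 65% under the assumed inputs, and uptake is unknown, so the loss may be negligible or material. Neither the primary endpoint nor the sample size is called into question. This is a worthwhile and inexpensive improvement to one secondary analysis.

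**What to change.** - Reconcile the two parts of Protocol 10.1, together with the synopsis and section 5, so that they agree on the schedule or schedules allowed in titration. Which one should apply is not a matter for this review.
- In SAP 8.2, derive each entrant's dosing frequency immediately before week 12. SAP 7.6 says the patient card records date and dose, so no new data are needed.
- Run the twice-weekly-to-weekly analysis on patients dosed twice weekly immediately before week 12, and keep the all-entrants result beside it.
- Describe patients already on weekly dosing separately, and tabulate their number by arm. If the count is zero, the matter is closed.

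The cost is SAP wording and one derived variable. The drawback is a smaller set, selected on events after baseline, for one within-arm analysis. The SAP sample size section reports 43 enrolled (23 and 20), and maintenance takes only the responders among them. The restricted result should therefore be read descriptively and never without the all-entrants result.
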